5.5.2. Missed Clinic Visits/Lost to Follow-up

The following actions must be taken when a subject fails to attend the clinic for a required study visit:

- The site must attempt to contact the subject and re-schedule the missed visit as soon as possible.
- The site must counsel the subject on the importance of maintaining the assigned visit schedule and ascertain whether or not the subject wishes to and/or should continue in the study.
- In cases where the subject is deemed ‘lost to follow up’, the investigator or designee must make every effort to regain contact with the subject (where possible, 3 telephone calls and if necessary a certified letter to the subject’s last known mailing address or local equivalent methods). These contact attempts should be documented in the subject’s medical record.

- Should the subject continue to be unreachable, only then will he/she be considered to have withdrawn from the study with a primary reason of “Lost to Follow-up”.

[figure not shown]
5.5.3. Liver Chemistry Stopping Criteria

Liver chemistry stopping and increased monitoring criteria have been designed to assure subject safety and evaluate liver event etiology (in alignment with the Food and Drug Administration [FDA] premarketing clinical liver safety guidance).

Discontinuation of study intervention for abnormal liver tests is required when:

- a participant meets one of the conditions outlined in the algorithm below.
- when in the presence of abnormal liver chemistries not meeting protocol-specified stopping rules, the investigator believes study intervention discontinuation is in the best interest of the participant.

Phase II Liver Chemistry Stopping and Increased Monitoring Algorithm

Liver Safety Required Actions and Follow up Assessments Section can be found in Section [12.2](#).

5.5.3.1. Study Treatment Restart or Rechallenge

Study treatment restart or rechallenge after liver chemistry stopping criteria are met by any subject participating in this study is not allowed.

5.6. Subject and Study Completion

A completed subject is one who has completed all phases of the study including the Follow-up visit.

The end of the study is defined as the last subject's last visit.

6. STUDY TREATMENT

6.1. Investigational Product and Other Study Treatment

The term 'study treatment' is used throughout the protocol to describe any combination of products received by the subject as per the protocol design. Study treatment may therefore refer to the individual study treatments or the combination of those study treatments.

Product name:	Daprodustat
Dosage form:	Tablet
Unit dose strength(s)/Dosage level(s):	1 mg, 2 mg, 4 mg, 6 mg, 8 mg, 10 mg tablet strengths/1 mg, 2 mg, 4 mg, 6 mg, 10 mg, 12 mg & 24 mg dosage levels
Route of Administration	Oral
Physical description:	1 mg, 2 mg & 4 mg tablets: 7.0 mm round, compound radius, white film coated tablets 6 mg, 8 mg & 10 mg tablets: 9.0 mm round, compound radius, white film coated tablets
Method for individualizing dosage:	See Section 6.4.1

For a description of epoetin alfa, please consult the local label.

All eligible subjects will discontinue their current ESA therapy and will undergo a 2-week ESA washout period. Following washout, subjects will be randomized to receive either daprodustat or epoetin alfa, on a dialysis day. For subjects with a three-time weekly dialysis schedule, randomization must not occur on the first dialysis session of the week (e.g., if Monday-Wednesday-Friday schedule, the study visit cannot be on Monday). For subjects with a four to five times weekly dialysis schedule, randomization can be on any hemodialysis session of the week.

Subjects can take their tablets without regard to food. For all study visits, it is recommended for subjects not to eat a heavy meal before coming to the clinic in order to avoid lipemia of the blood sample collected for the analysis of transferrin, iron and total iron binding capacity (TIBC).

6.2. Treatment Assignment

Subjects will be stratified by prior ESA dose (as outlined in Section [4.1](#)) and randomized 1:1 to receive open-label oral daprodustat or IV epoetin alfa. A central randomization approach will be used due to the small sample size and to protect against potential selection bias due to the open-label design. Once a randomization number has been assigned by an Interactive Voice/Web Response System (IVWRS) at time of Randomization, it must not be re-assigned.

Subjects will be assigned to study medication in accordance with the randomization schedule generated by Clinical Statistics, prior to the start of the study, using validated internal software.

6.3. Blinding

This will be an open-label study. However, there are no plans to generate any aggregated unblinded summaries during the conduct of the study.

6.4. Starting Dose and Dose Adjustment Algorithm

6.4.1. Subjects Randomized to Daprodustat

Subjects randomized to daprodustat will have doses adjusted, as required, to target Hgb within the range of 10.0-11.0 g/dL. Dose adjustments will be assigned **automatically** via the IVWRS based on the subject's Hgb value via onsite HemoCue assessment according to the following algorithms:

Day 1 (HemoCue Prior to Acute Challenge 1)

Hgb (g/dL)	Action or Dose
<7.5	Repeat HemoCue assessment on the same sample at same study visit to confirm; take average of 2 values. If confirmed, withdraw subject from the study.
≥7.5 and <10.0	6 mg daprodustat
≥10.0 and <11.5	4 mg daprodustat
≥11.5	Repeat HemoCue assessment on the same sample at same study visit to confirm; take average of 2 values. If confirmed, avoid dosing and continue washout for one additional week. If Hgb remains above 11.5 then withdraw subject from study.

The 8 week Hgb maintenance dosing will begin on Day 2, following Acute Challenge 1. Acute Challenge dosing is the same for all subjects on the daprodustat arm: 24 mg.

Days 15, 29, 43, & 57

The available dose steps for daprodustat are outlined below (highlighted boxes indicate starting doses). Dose adjustments will result in the daprodustat dose being increased or decreased by **one dose step**.

Hgb (g/dL)	Hgb change since previous study visit	Dose Adjustment
<7.5	Any change	Repeat HemoCue assessment on the same sample at same study visit to confirm; take average of 2 values. If confirmed, permanently discontinue study drug and withdraw subject from the study.
≥7.5 to <9.5	Decreasing or No change ¹	Increase to the next higher dose step
≥7.5 to <9.5	Increasing ²	Maintain dose

≥9.5 to ≤11.5	Any change	Maintain dose
>11.5 to <12.0	Increasing or No change	Decrease to the next lower dose step
	Decreasing	Maintain dose
≥12.0	Any change	Repeat HemoCue assessment on the same sample at same study visit to confirm; take average of 2 values. If confirmed, HOLD dosing for 2 weeks until next study visit. ³
≥7.5 to <12.0	increase of ≥1.3 in Hgb over 2 weeks ⁴	Repeat HemoCue assessment on the same sample at same study visit to confirm; take average of 2 values. If confirmed, decrease to next lower dose step,
≥7.5 to <12.0	Increase of > 2.0 in Hgb over previous 4 weeks (Days 29, 43, 57 ⁴ only)	Repeat HemoCue assessment on the same sample at same study visit to confirm; take average of 2 values. If confirmed, decrease to next lower dose step,

¹No change is defined as an increase < 0.5 g/dL

²Increase is defined as an increase ≥ 0.5 g/dL

³ If Hgb remains ≥12.0 at next visit, the subject should be withdrawn from the study. If the Hgb drops below 12.0, the subject should be restarted on the next lowest dose.

⁴ Only applies at Day 57 if a repeat AC2 is necessary. The dose should be decreased for the 1 week between AC2 and Additional AC2.

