On Day 57, following the 8-week Hgb maintenance period, subjects will undergo Acute Challenge 2; this challenge will, similar to Acute Challenge 1, involve assessing the effect of daprodustat and epoetin alfa on BP as assessed by 24-hr ABPM measurement. The subjects will be administered the same dose of either daprodustat or epoetin alfa that was given in Acute Challenge 1, and serial blood sampling will be performed to assess daprodustat pharmacokinetics, and to characterize the time course of various biomarkers. Acute Challenge 2 will be started following completion of a mid-week dialysis session.

Subjects will attend a follow-up visit 2 weeks after completion of Acute Challenge 2. Subjects will be asked to not reinitiate anemia treatment until after the follow-up visit unless deemed medically necessary.

After both Acute Challenge 1 and 2, the 24-hr ABPM results will be checked for data quality as defined in the Project Requirement Specification (PRS). If the ABPM fails the QC criteria following Acute Challenge 2, one additional Acute Challenge may be made after a subsequent, mid-week dialysis visit 1 week later if the subject agrees. At that visit, the subject will receive the same study treatment for the repeat Acute Challenge 2 as was administered on Day 57 as a single additional dose. No additional clinical chemistry, hematology, pharmacokinetic or biomarker sampling will be done, however all other procedures will be performed as detailed in [Table 4](#).

The Acute Challenge 2 may be delayed one week if the subject's Hgb ≥ 11.5 . See Section [7.5.1.1](#) for guidance.

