7.1. Time and Events Table
Table 3 Study Procedures and Assessments

Procedure ¹	Screening	Washout	Treatment Period ²					Follow-up ²	
			Day 1	Day 15	Day 29	Day 43	Day 57	Early WD	Week 10
Informed Consent	X								
Entry Criteria	X								
Physical, Medical History, Demography	X								
HemoCue Hgb	X	X	X ⁴	X	X	X	X ⁴	X	X
Enrolment		X							
IVWRS			X	X	X	X			
Randomization			X						
Acute Challenge			X ⁴				X ⁴		
ABPM Assessment			X ⁴				X ⁴		
Dose Adjustment				X	X	X			
Females Only: Serum Pregnancy Test	X		X		X		X		X
Females Only: Estradiol & FSH (if required) ³	X								
ECG	X		X ⁴				X ⁴		X
Vital signs & weight (Pre- & Post-dialysis)	X	X	X ⁴		X		X ⁴		X
Clinical Chemistry	X		X		X		X		X
Hematology	X		X		X		X		X
Folate and Vitamin B12	X								
Ferritin, transferrin, total iron, TSAT, UIBC	X								
Pharmacokinetic/Biomarker Assessments			X ⁴				X ⁴		
Hgb Maintenance Period ⁵			←-----→						
Adverse Events Assessment	X ⁶	X	X ⁴	X	X	X	X ⁴		X
Review Concomitant Medications	X	X	X ⁴	X	X	X	X ⁴		X

1 All assessments should be done predialysis/predose except as noted.

2 Allowable time window ± 2 days EXCEPT Follow-up Visit which is ± 3 days.

3 As detailed in Inclusion Criteria.

4 Detailed timings for assessments on Acute Challenge Days are given in [Table 4](#).

5 From the end of Acute Challenge 1 to the beginning of Acute Challenge 2.

6 Only SAEs assessed as related to study participation are collected at this visit. See Section [12.4](#) for additional details.

Table 4 Study Procedures and Assessments on Acute Challenge Days (Treatment Period Day 1 and Day 57)

Procedure	Pre-Dialysis	Post-Dialysis	Predose	Time (in hours relative to dosing)										
				0	0.5	1	2	3	4	6	8	12	16	24
HemoCue Hgb ¹			X											X
IVWRS			X											
ABPM Assessment ^{1,3}			←=====→											
Administer Study Treatment ¹				X										
Serum Pregnancy Test ¹			X											
ECG ¹			X											X
Vital Signs and Weight ¹	X	X						X				X		X
Clinical Chemistry			X											
Hematology			X											
Pharmacokinetics ⁴			X		X	X	X	X	X	X	X	X	X	X
Erythropoietin			X		X	X	X	X	X	X	X	X	X	X
Endothelin-1			X		X	X		X	X	X				X
Nitric Oxide			X		X	X		X	X	X				X
Asymmetric dimethylarginine			X		X	X		X	X	X				X
Renin			X		X	X		X	X	X				X
Angiotensin-II			X		X	X		X	X	X				X
Noradrenalin			X		X	X		X	X	X				X
Adverse Events Assessment ¹			X		X	X	X	X	X	X	X	X	X	X
Review Concomitant Medications ¹			X											X
Initiate Hgb maintenance dosing ²														X

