1 Procedures to be repeated if Acute Challenge 2 fails quality control criteria (For more detail refer to Section 7.5.1)

2 Applies to Acute Challenge 1 only

3 Timing of ABPM measurements does not correlate with specified time points in Table 4.

4 PK to be drawn from daprodustat subjects only.

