7.5. Biomarker(s)/Pharmacodynamic Markers

7.5.1. Ambulatory Blood Pressure Monitoring (ABPM)

Blood pressure and pulse will be measured during Acute Challenge 1 and 2 through the use of an ambulatory blood pressure monitoring device. Subjects will wear the ABPM device for two sessions during the study (i.e., Acute Challenge 1 and 2), occurring at Day 1 (randomization) and at Day 57. The ABPM device will be placed prior to Acute Challenge dosing, and will remain on the subject's arm until 24 hrs post-dosing.

ABPM measurements of systolic and diastolic blood pressure and heart rate will be automatically recorded every 15 minutes for the first 6 hrs post-dosing, and then every 20 minutes thereafter until 24 hrs post-dosing. The ABPM device will automatically calculate MAP.

The device planned for use in this study is the Mortara Ambulo 2400; a specification sheet for this device can be found in Section [12.6](#).

After both Acute Challenge 1 and 2, the 24-hr ABPM results will be checked for data quality as defined in the Project Requirement Specification (PRS). If the ABPM fails the QC criteria following Acute Challenge 2, one additional Acute Challenge may be made in a subsequent, mid-week dialysis visit 1 week later if the subject agrees. At that visit, the subject will receive the same study treatment for the repeat Acute Challenge 2 as was administered on Day 57 as a single additional dose. No additional clinical chemistry, hematology, pharmacokinetic or biomarker sampling will be done, however all other procedures will be performed as detailed in [Table 4](#).

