## 5. CONSIDERATIONS FOR DATA ANALYSES AND DATA HANDLING CONVENTIONS

### 5.1. Study Treatment & Sub-group Display Descriptors

Treatment Group Descriptions			
[RandAll NG / FSO Randomization System]		Data Displays for Reporting	
Code	Description	Description	Order in TLF
A	IV epoetin alfa	rhEPO	2
B	Daprodustat	Dapro	1
-	-	Total	3

Treatment comparisons will be displayed as follows using the descriptors as specified:

Dapro vs rhEPO

Within each treatment group/arm, the display descriptors for the study periods/visits will be as follows:

Pre-Protocol Amendment 3	Post-Protocol Amendment 3
Study Period (Visit)	Study Period (Visit)
Screening* (Week -8 to Week -4)	Screening* (7-30 days prior to Week -2)
ESA Washout* (Week -4 to Day 1)	ESA Washout* (Week -2 to Day 1)
Acute Challenge 1 (Day 1)	Acute Challenge 1 (Day 1)
Hgb Maintenance Phase (Day 2 to Day 56)	Hgb Maintenance Phase (Day 2 to Day 56)
Acute Challenge 2 (Day 57)	Acute Challenge 2 (Day 57)
Hgb Maintenance Phase (Day 58 to day before repeated AC2)	Hgb Maintenance Phase (Day 58 to day before repeated AC2)
Repeat Acute Challenge 2**	Repeat Acute Challenge 2**
Early Withdrawal	Early Withdrawal
Follow-up (Day 58 to Week 10)	Follow-up (Day 58 to Week 10)

\*For these visits, the period will include the first visit up to but not including the last reference visit. For example, screening period for pre-protocol amendment 3 will be defined as week -8 up to but not including the week -4 visit.

CONFIDENTIAL

205665

\*\*For subjects with a repeat acute challenge 2, the follow-up period will be the day following this visit

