**CONFIDENTIAL**

205665

A listing of which participants reported specific adverse events will be produced.

The hierarchical relationship between MedDRA SOCs, PTs and verbatim text will be listed for all adverse events.

Adverse events occurring during the 24-hour acute challenge will be grouped in the appropriate acute challenge phase. Any AE occurring after AC2 but before repeat-AC2 will be grouped in the HGB maintenance phase.

Adverse events occurring after the last on treatment date will be grouped either in early withdrawal or follow-up depending on the final status of the subject,

*Serious and Other Significant Adverse Events*

The number and percentage of participants and the number of occurrences of SAEs will be provided for each treatment group. These events will be summarized by treatment group, primary system organ class, and preferred term. Pre-treatment, post-randomization, treatment emergent and follow-up SAEs will be summarized separately. Treatment emergent SAE preferred terms will also be summarized by treatment group and overall frequency.

A listing of reasons for considering as a SAE will be produced for all treatment emergent SAEs.

The number and percentage of participants and the number of occurrences of treatment emergent drug-related SAEs, and drug-related fatal SAEs will be summarized by treatment group.

A listing of treatment emergent fatal SAE records and a listing of treatment emergent non-fatal SAE records will be provided.

The number and percentage of participants reporting treatment emergent AEs leading to discontinuation of randomized treatment will be summarized by treatment group, primary system organ class, and preferred term.

A listing of treatment emergent AEs leading to discontinuation of randomized treatment will be provided.

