#### 11.1.4. Strategy for Intercurrent (Post-Randomization) Events

ABPM data is collected every 15 minutes for the first 6-hrs and then every 20 minutes thereafter until 24-hrs post dose. In order to reduce the extent of missing ABPM data due to device issues, the device is designed to retry measuring blood pressure if it fails to record a BP during the scheduled timepoint. In addition, after both Acute Challenge 1 and 2, the 24-hr ABPM results will be checked for data quality as defined in the Project Requirement Specification (PRS). If the ABPM fails the QC criteria following Acute Challenge 2, one additional Acute Challenge may be made in a subsequent, mid-week dialysis visit 1 week later if the participant agrees. This repeat Acute Challenge 2 would replace the failed QC Acute Challenge 2.

For these participants who have a failed QC of the ABPM for a given acute challenge day, the data that is available from the ABPM device will be used during a sensitivity analysis on the primary endpoint. For those participants that fail QC both Acute Challenge 2, and a repeat Acute Challenge 2, the repeat Acute Challenge 2 data will be utilized.

Since participants who discontinue randomized study medication are withdrawn from the study and would have already performed their Day 1 acute challenge, multiple imputation will be used to attempt to impute what the missing data would have been had the participant not stopped randomized study medication. These participants who are early withdrawn will have their missing Day 57 ABPM data imputed to be included in a sensitivity analysis on the primary endpoint. This sensitivity analysis will include those participants who both early withdrawal and have their ABPM data imputed as well as those participants whose ABPM data did not pass QC for a given day. Details of the multiple imputation can be found in Section 14.6.6.

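### The documents disagree on whether maintenance treatment continues in the week between a QC-failed Acute Challenge 2 and its repeat

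*Protocol*

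**What the plan says.** Protocol 4.1 and 7.5.1 allow one repeat of AC2, a week later, if the Day 57 ambulatory recording fails quality control and the subject agrees. The subject then receives the same challenge treatment "as was administered on Day 57 as a single additional dose". SAP 11.1.4 states how the repeat is used: "This repeat Acute Challenge 2 would replace the failed QC Acute Challenge 2". The hypothesis in protocol 9.1 and SAP 2.4 is about the AC2 difference while subjects are on background treatment.

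Texts implying that maintenance dosing continues in the intervening week:
- Protocol 6.4.1 includes Day 57 in the heading of its dose-adjustment table. Footnote 4, attached to the rapid-rise rows, reads "The dose should be decreased for the 1 week between AC2 and Additional AC2".
- SAP 5.1 lists, for each arm, a period "Hgb Maintenance Phase (Day 58 to day before repeated AC2", and starts follow-up the day after the repeat.
- SAP 8.1: "Any AE occurring after AC2 but before repeat-AC2 will be grouped in the HGB maintenance phase".
- SAP 14.6.2 extends planned treatment duration to the repeat Day 57 where there is one.

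Texts implying that it has ended:
- Protocol Table 3, footnote 5, defines the maintenance period as "From the end of Acute Challenge 1 to the beginning of Acute Challenge 2".
- Table 3 has no Dose Adjustment or IVWRS mark on Day 57.
- The SAP 6.2.1 disposition table ends maintenance at Day 57 and starts follow-up on Day 58, with no row for a repeat.
- SAP 8.1 also defines maintenance as the time between challenges 1 and 2.

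Two further passages bear on the week without settling it. Protocol 4.1 says "Subjects will be asked to not reinitiate anemia treatment until after the follow-up visit unless deemed medically necessary". Table 4, footnote 2, on the row for starting maintenance dosing, says "Applies to Acute Challenge 1 only". Protocol 6.4.2 has epoetin alfa dosed by local labelling and practice guidelines and does not mention this week.

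**The concern.** A site cannot follow both sets of passages. One that works from Table 3 would treat maintenance as finished on Day 57 and do the repeat with no maintenance treatment since the Day 57 challenge dose. One that works from 6.4.1 would do the repeat on maintenance. In the epoetin arm the protocol gives no explicit instruction for the week.

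The repeat value enters the primary analysis in place of the failed one, and the hypothesis is specific to a treated background. For repeat subjects, then, the condition under which the primary endpoint is measured could vary by site and by arm. No planned table would show it. The sensitivity analyses in SAP 11.1.5.2 cover the per-protocol set, imputed and QC-failed data, and 8-, 12- and 24-hour averages; none isolates repeats. Table 4.42 counts QC passes with Day 57 and repeat Day 57 merged.

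**Working it through.** **Step 1: can the ended side be read as consistent with continued dosing?**
- The single-dose wording in 4.1 and 7.5.1 can describe only the repeat challenge dose. No conflict on that reading.
- The request in 4.1 about anemia treatment follows the sentence on the follow-up visit, so it can mean the time after the last challenge. No conflict on that reading.
- Table 4, footnote 2, concerns starting maintenance. Continuing is not starting. No conflict on that reading.
- Table 3, footnote 5, gives an end point for the maintenance period with no extension for a repeat. The conflict remains.
- Table 3 has no Day 57 mark for Dose Adjustment, while 6.4.1 names Day 57 as an adjustment visit. The conflict remains.
- SAP 6.2.1, and the definition of maintenance in SAP 8.1, conflict with SAP 5.1 and with the adverse-event rule in SAP 8.1 itself. The conflict remains.

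**Step 2: can the continuing side be read as consistent with stopping?** No. A dose can be decreased for a week only if it is being taken. The Day 57 entry in 6.4.1 also has little else to act on, since no maintenance dosing follows an AC2 that passes quality control.

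**Step 3: by group.**
- Daprodustat, rapid Hgb rise: 6.4.1 footnote 4 is explicit for dosing; Table 3 implies none.
- Daprodustat, all others: the Day 57 rows of 6.4.1 that keep or raise the dose, and SAP 5.1, imply dosing; Table 3 implies none.
- Epoetin alfa: SAP 5.1 implies dosing; Table 3 implies none; 6.4.2 does not address the week.

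**Step 4: operation.** Under 6.4.1, daprodustat doses are assigned through the IVWRS. Table 4 marks an IVWRS contact before dosing on both challenge days, but Table 3 does not mark Day 57. The need for a repeat is known only after the 24-hour recording is checked, and neither table schedules a later IVWRS contact.

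**Step 5: doses in question.** A repeat 7 days after Day 57 falls on Day 64. The days between are 58 to 63: 63 − 58 + 1 = 6 daily daprodustat doses, before visit windows.

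**Step 6: scale.** The plan's own figure first (protocol 9.2.1): 25 per arm, SD 16 mmHg, difference 15 mmHg, two-sided 5%. Standard error = 16 × √(2/25) = 4.53. Half-width = t(0.975, 48 df) × 4.53 = 9.10 mmHg, against 9.1 stated. Noncentral-t power = 90.1%, against 90% in Table 6. The plan's figures reproduce.

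The documents give neither a repeat rate nor an effect of a week without maintenance, so what follows is assumption only. If 5% to 20% of the 50 analysed AC2 values were repeats, that is 0.05 × 50 = 2.5 to 0.20 × 50 = 10 values. If a share f of subjects had a repeat off maintenance and the 15 mmHg contrast were reduced by a fraction a in them, the overall contrast would be d = 15 × (1 − f × a):

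| f | a | d (mmHg) | Power |
|---|---|---|---|
| 5% | 50% | 14.62 | 88.6% |
| 10% | 50% | 14.25 | 87.0% |
| 20% | 50% | 13.50 | 83.2% |
| 20% | 100% | 12.00 | 73.8% |

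These rows show only how the result would scale. They are not evidence that it happens.

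**The case against.** The strongest reply is that this is a drafting inconsistency with a discernible intention. The Day 57 entry and footnote 4 in 6.4.1 were added by Amendment 4 and speak directly to the repeat. SAP 5.1, one rule in 8.1, and 14.6.2 agree with them. Table 3 has no repeat column and can be taken as the nominal schedule. This has force, but a schedule table with a footnoted end point is what sites work from, the SAP contradicts itself, and nothing explicit in the protocol covers epoetin alfa.

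Three stronger readings are tempting and should not be drawn.
- A reader might infer that, apart from footnote 4, every applicable text points to no treatment. It does not: the Day 57 rows of 6.4.1 reach daprodustat subjects without a rapid rise, SAP 5.1 applies to both arms, and 6.4.2 contains no stop at Day 57.
- A reader might equate the week with half of the 14-day ESA washout. That ignores the full challenge dose on Day 57. For epoetin alfa this is 100 U/kg, against mean weekly doses of 89 and 102 IU/kg in the earlier study cited in protocol 4.5: 100/89 = 1.12 and 100/102 = 0.98 of a week's dose. The protocol also accepts AC2 data after a one-week hold when Day 57 Hgb is 11.5 g/dL or more (Table 2; 7.5.1.1). That hold, however, is one explicit Hgb-triggered rule for both arms, which is what the repeat week lacks.
- A reader might infer a distortion of adverse-event counts. Under SAP 14.4.2, events during treatment interruptions are treatment emergent in any case, so only the phase label is affected.

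The assumed 5% to 20% also has a limit: 50 is the number expected to complete and pass QC, and a repeat needs the subject's agreement, so QC failures and repeats are not the same count.

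**Conclusion.** The inconsistency is real and lies in current text. Protocol 6.4.1 and parts of SAP 5.1, 8.1 and 14.6.2 have maintenance continuing to the repeat; protocol Table 3, SAP 6.2.1 and another part of SAP 8.1 have it ended at AC2. The wording in 4.1 is ambiguous, and 6.4.2 is silent for epoetin alfa. Because the repeat replaces the failed recording in the primary analysis, background treatment at the primary measurement could differ between sites and arms for those subjects.

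The number of such subjects is not in the documents, and the size and direction of any effect are unknown. A reader might infer that the primary result is biased; the documents do not support that. What they support is that a condition of the primary measurement is not uniquely specified and that no planned analysis would reveal the consequence. It should be corrected, but it does not call the design into question.

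**What to change.** State one rule, covering both arms, for maintenance treatment between Day 57 and a repeat AC2. Reconcile to it protocol 4.1, 6.4.1 footnote 4, 6.4.2, 7.5.1, Table 3 (footnote 5 and the Day 57 marks) and Table 4 footnote 2, and SAP 5.1, 6.2.1 and 8.1. Which rule is right is for the sponsor; this review does not say.

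Derive whether each repeat subject was on or off maintenance before the repeat. Protocol 6.7 already has daprodustat dosing details and tablet counts, and dated epoetin alfa doses in the source documents; SAP 6.2.6 lists dose start and stop dates. Check that the epoetin alfa dates reach the analysis data. Add one sensitivity run of the primary model excluding repeat-AC2 subjects, and report the number of repeats by arm.

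The cost is amendment wording and one extra table, with no added subjects or visits. If all subjects have already completed, the derivation and the sensitivity run can still be done.
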